12.10 Liver Biopsy Substudy - Years 1-7

For the optional liver biopsy substudy (refer to Table 9.1.7), the following procedures will be performed at the following times:

- Within 28 days before Biopsy Day
 - o Informed consent
 - Liver ultrasound
 - Liver ultrasound does not need to be performed if an ultrasound result from the prior 3 months is already available
 - Brief physical examination
 - Hematology, Coagulation, and Chemistry Assessments (refer to Table 9.7.9.2.1)
 - Liver Tests (refer to Table 9.7.9.3.1)
- Within 7 Days before Biopsy Day
 - o FibroScan
 - Local laboratory FVIII activity level assessment
 - Pre-biopsy consultation with investigator (treating hematologist). This may need to be repeated/extended if the subject's FVIII activity levels need adjustment before the biopsy, at the discretion of the investigator (treating hematologist).
- 1 Day before Biopsy Day
 - Hematology, Coagulation, and Chemistry Assessments (refer to Table 9.7.9.2.1)
 - Liver Tests (refer to Table 9.7.9.3.1) local laboratory assessment
 - Brief physical examination

270-201 Amendment 10

- o Local laboratory FVIII activity level assessment
 - Subjects must have a FVIII activity level of at least 50 IU/dL (or higher, depending on local guidelines and/or investigator discretion). As needed, subjects may be treated with additional exogenous FVIII replacement products in order to increase their FVIII activity levels to an appropriate level, under the supervision/instruction of the investigator, to ensure the safety of the subject during the procedure. This exogenous FVIII usage (if performed) should be recorded in the eCRF FVIII infusion pages under the category "Surgery/Procedure".
- Biopsy Day
 - Brief physical examination
 - Local laboratory FVIII activity level assessment (performed pre-biopsy)
 - Subjects must have a FVIII activity level of at least 50 IU/dL (or higher, depending on local guidelines and/or investigator discretion). As needed, subjects may be treated with additional exogenous FVIII replacement products in order to increase their FVIII activity levels to an appropriate level, under the supervision/instruction of the investigator, to ensure the safety of the subject during the procedure. This exogenous FVIII usage (if performed) should be recorded in the eCRF FVIII infusion pages under the category "Surgery/Procedure".
 - Liver Tests (refer to Table 9.7.9.3.1) local laboratory assessment (pre-biopsy)
 - Liver Biopsy (refer to Laboratory Manual for guidelines for biopsy procedure and handling of biopsy samples)
 - If only a small amount of tissue is obtained at the time of the biopsy, the subject may be asked to consent for a second pass.

Following completion of the biopsy, the subject should remain in the hospital under observation for at least 4-6 hours. Overnight post-procedure observation may be done at the investigator's discretion.

Participation in the substudy may include liver biopsies at one or more time points.

12.11 Early Termination Visit

The Early Termination visit will occur on the date the subject withdraws from the study, even if the date does not correspond to a protocol-specific visit.

BIOMARIN[®] 270-201 Amendment 10

If a subject leaves the study prior to the Week 364 visit, the subject will be asked to return to the study site and complete an Early Termination visit. At the Early Termination visit, as many of the following assessments as possible should be done:

- Physical examination
- Assessment of Adverse Events and Concomitant Medications (including review of subject diary for bleeding and FVIII use)
- Vital Signs
- Blood chemistry, haematology, coagulation screen, and CRP (refer to Table 9.7.9.2.1)
- Urine Tests (refer to Table 9.7.9.2.1)
- Liver Tests (refer to Table 9.7.9.3.1) local laboratory assessment
- FVIII activity level local laboratory assessment
 - FVIII activity level (one-stage clotting assay)
 - FVIII activity level (chromogenic substrate assay)
- Liver Tests (refer to Table 9.7.9.3.1) central laboratory assessment
- FVIII Assays central laboratory assessment
 - FVIII activity level (one-stage clotting assay)
 - FVIII activity level (chromogenic substrate assay)
 - o FVIII coagulation activity exploratory assay
 - Bethesda assay (with Nijmegen modification) for FVIII inhibitor level

Note: If a subject has used FVIII within 72 hours of a measurement day, all efforts should be made to obtain FVIII activity measurements when a 72-hour interval without FVIII use is achieved; the 72-hour wash-out period is only intended for subjects who have achieved FVIII \geq 5 IU/dL at 16 weeks after BMN 270 infusion and who have not resumed standard of care FVIII replacement therapy.

- FVIII antigen (ELISA)
- AAV5 antibody titer
- FVIII antibody titer
- PBMC collection
- VWF:Ag

- Liver ultrasound
- PCR of vector DNA in blood, saliva, urine, semen, and stools
 - Sample testing at the ETV is not required if at least 3 consecutive samples are below the limit of detection prior to the ETV.
- Exploratory biomarker assessment
- Haemo-QoL-A QOL assessment

12.12 End of Study

The study will end after the last subject completes the last Safety Follow-Up visit (Week 364). BioMarin reserves the right to discontinue the study any time for clinical or administrative reasons and to discontinue participation of an individual investigator or site for clinical or administrative reasons, including, but not limited to, poor enrollment or noncompliance with procedures of the protocol or GCP. In addition, the study may be terminated if, in the opinion of BioMarin, the safety of the study subjects may be compromised.

BOMARIN[®] 270-201 Amendment 10

13 DATA QUALITY ASSURANCE

BioMarin personnel or designees will visit the study site prior to initiation of the study to review with the site personnel information about the IP, protocol and other regulatory document requirements, any applicable randomization procedures, source document requirements, eCRFs, monitoring requirements, and procedures for reporting AEs, including SAEs.

At visits during and after the study, a CRA will monitor the site for compliance with regulatory documentation, with a focus on accurate and complete recording of data on eCRFs from source documents, adherence to protocol, randomization (if applicable), SAE reporting and drug accountability records.

Data quality control and analysis will be performed by BioMarin or a designee, based on a predefined analysis plan.

BOMARIN[®] 270-201 Amendment 10

14 STATISTICAL METHODS AND DETERMINATION OF SAMPLE SIZE

14.1 Statistical and Analytical Plans

The statistical analysis plan (SAP) will provide additional details on the planned statistical analysis. Unless otherwise stated, all analyses will be performed using SAS.

14.1.1 Interim Analyses

No formal interim analysis is planned. An analysis of the primary endpoint will be done following all subjects having completed the study assessments through the end of the Post-Infusion Follow-Up Period (Week 16).

14.1.2 Procedures for Accounting for Missing, Unused and Spurious Data

Missing data will not be imputed.

14.2 Primary and Secondary Efficacy Analysis

The subjects will be followed in a longitudinal manner and all the relevant information will be collected. The analysis of the data will be descriptive in nature. Descriptive statistics include the number of subjects, mean, median, standard deviation, minimum, and maximum for continuous variables and count and percent for categorical variables. Efficacy variables will be summarized by dose cohort at each time point. Relationship between dose and efficacy results will be examined.

Data collected in a longitudinal manner may be analyzed using longitudinal methods such as mixed effect model which takes into account the correlation among the observation taken at various time points within a participant. Efficacy is a secondary endpoint, defined as biologically active hFVIII at ≥ 5 IU/dL by chromogenic substrate assay and/or one-stage clotting assay as measured by the central laboratory at 16 weeks following study treatment. We can only assess the true steady state of hFVIII protein produced from BMN 270 after a minimum of 72 hours has elapsed since the last infusion of FVIII protein concentrates.

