7 INTRODUCTION

Haemophilia A (HA) is an X-linked recessive bleeding disorder that affects approximately 1 in 5,000 males (Iorio 2019). It is caused by mutations in the factor VIII (FVIII) gene that codes for FVIII protein, an essential cofactor in the coagulation cascade. Clinical manifestations of severe FVIII deficiency are frequent unprovoked bleeding episodes in joints and soft tissues causing permanent disability and occasionally death mostly after brain haemorrhage. Treatment in Western (Berntorp 2012) countries consists of intravenous injection of plasma derived or recombinant FVIII protein concentrates at the time of a bleed, or prophylactically, to prevent bleeding episodes. The short half-life for FVIII (~8-12 hours) necessitates frequent infusions and makes this treatment prohibitively expensive for the majority of the world's haemophilia A patients. These individuals develop debilitating arthropathy and have a substantially increased risk of death from haemorrhage in life (Stonebraker 2010). Chemical modification or bioengineering of FVIII may improve half-life to 18-19 hours (Kaufman 2013). However, these long acting FVIII variants do not eliminate the need for lifelong FVIII protein administration (Hay 2012).

Gene therapy offers the potential of disease-modifying therapy by continuous endogenous production of human FVIII following a single administration of vector. Haemophilia A is well suited for this approach because its clinical manifestations are attributable to the lack of a single gene product (FVIII) that circulates in low amounts (100-200 ng/ml) in the plasma. Tightly regulated control of gene expression is not essential and a modest increase in the level of FVIII (a plasma level of 2 ng/ml protein leads to a 1% expression) can ameliorate the severe phenotype (Srivastava 2020); thus the therapeutic goal for gene therapy is a modest increase in hFVIII. Finally, the consequences of gene transfer can be assessed using simple quantitative rather than qualitative endpoints that can be easily assayed in most clinical laboratories.

BMN 270 contains the cDNA for the B-domain deleted SQ FVIII with a liver-specific HLP transcription promoter. The expression cassette is inserted between AAV2 ITRs and this genome is packaged in the AAV5 capsid. A comprehensive review of BMN 270 is contained in the IB supplied by BioMarin. Investigators are to review this document prior to initiating this study.

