7.3 Study Rationale

Haemophilia A (HA) is an X-linked recessive bleeding disorder that affects approximately 1 in 5,000 males (Iorio 2019). It is caused by deficiency in the activity of coagulation factor VIII (FVIII), an essential cofactor in the intrinsic coagulation cascade. This disorder can be either inherited, due to a new mutation or an acquired immunologic process, leading to insufficient quantities of FVIII or a dysfunctional FVIII, but all are characterized by a defective coagulation process. The clinical phenotype of HA patients is largely governed by the level of residual expression. Severe HA is classified as FVIII activity less than 1% of wild type (< 1 IU/dL), moderate disease comprises 1-5% of wild type activity and the mild form is 5-40% activity. The clinical manifestations of severe HA remain frequent spontaneous bleeding episodes, predominantly in joints and soft tissues, with a substantially increased risk of death from haemorrhage when the brain is involved.

Treatment of severe HA presently consists of intravenous injection of plasma derived or recombinant human FVIII protein (rhFVIII) concentrates both as prophylaxis 2-4 times per week, and at the time of a bleed, to prevent or control bleeding episodes, respectively. The half-life for FVIII (12-18 hours for most approved products) necessitates frequent infusions, and although a major advance in the treatment of HA, it remains common for severe HA patients to continue to have multiple bleeding events on treatment (mean of 1 to 7 episodes/year with prophylaxis and up to 30 to 50 episodes/year for on demand treatment) (Nagel 2011). The consequence of multiple bleeding events is the development of an underlying pathology that contributes to debilitating multiple-joint arthropathy and

270-201 Amendment 10

[figure not shown]
Page 31

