substantially increased risk of death (Nagel, 2011, Haemophilia). Chemical modification (eg, direct conjugation of polyethylene glycol (PEG) polymers) and bioengineering of FVIII (eg, FVIII-Fc fusion proteins) improve half-life by approximately 50%, and thus, show promise in reduced dosing and maintaining activity levels above 1% trough (Stonebraker 2010; Mahlangu 2014). However, these longer acting FVIIIs remain dependent on multiple infusions to maintain critical levels of FVIII activity in severe HA patients. There is therefore a strong unmet need for a fully preventive treatment of HA to give patients a FVIII level compatible with a normal and haemorrhage-free life.

Gene therapy offers the potential of disease-modifying therapy by continuous endogenous production of active FVIII following a single intravenous administration of a vector with the appropriate gene sequence. Haemophilia A is well suited for a gene replacement approach because clinical manifestations are attributable to the lack of a single gene product (FVIII) that circulates in minute amounts (200 ng/ml) in the plasma. Tightly regulated control of gene expression is not essential, and modest increases in the level of FVIII (any increase of the plasma level by 2 ng/ml induces an increase in activity of 1%) can ameliorate the severe form of the disease. Thus, relatively small changes in endogenous FVIII activity results in clinically relevant improvements in disease phenotype. Finally, the response to gene transduction can be assessed using validated quantitative rather than qualitative endpoints that are easily assayed using established laboratory techniques.

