9.7.2 Primary Efficacy Variables

The primary efficacy measure will be the plasma FVIII activity monitored on a regular basis after BMN 270 dose. The efficacy goal of the protocol is to ascertain the dose range of BMN 270 required to convert severe HA patients to expression of FVIII at 5 IU/dL or above, (ie, a mild severity). This is associated in natural history studies with clinically superior long term outcomes (Den Ujil 2011).

The following assays (assessed by the central laboratory) will be used to measure the primary efficacy variable:

- FVIII activity (chromogenic substrate assay)
- FVIII activity by one-stage clotting assay

If a subject has used FVIII within 72 hours of a measurement day, all efforts should be made to obtain FVIII activity measurements when a 72-hour interval without FVIII use is achieved. The 72-hour wash-out period is only intended for subjects who have achieved FVIII ≥ 5 IU/dL at 16 weeks after BMN 270 infusion and who have not resumed standard of care FVIII replacement therapy.

The FVIII activity level in both assays and the number of subjects with FVIII activity ≥ 5 IU/dL in at least one of the two assays will be summarized.

FVIII activity assays will also be performed at the local laboratory at the time points indicated in Table 9.1.2, Table 9.1.3, Table 9.1.4, and Table 9.1.5 but will be used in conjunction with local lab LT assessments to monitor subject safety and need for initiation of reactive corticosteroid dosing; local laboratory FVIII activity assessments will not be used to assess efficacy or to measure the primary efficacy outcome of the study.

Subjects who do not respond to BMN 270 treatment (ie, treatment failure, manifesting as failure to achieve FVIII activity ≥ 5 IU/dL by Week 52 and inability to maintain independence from prophylactic FVIII replacement therapy due to joint bleeding episodes, in the judgment of the Investigator) may, at the Investigator's discretion and after discussion with the Medical Monitor, follow an abbreviated visit schedule after Week 52, as applicable and at the discretion of the Investigator.

Timing of assessment by these assays is provided in Table 9.1.2, Table 9.1.3, Table 9.1.4, and Table 9.1.5. Details on performing the assays are included in the Laboratory Manual.

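### The single 72-hour FVIII-free interval is too short for longer-acting products: at the stated 18-19 h half-lives it leaves 6-7% of the post-infusion peak, enough to reach 5 IU/dL from a peak of about 69-80 IU/dL

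*Protocol*

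**What the plan says.** Section 14.2 defines efficacy as FVIII of at least 5 IU/dL "by chromogenic substrate assay and/or one-stage clotting assay as measured by the central laboratory at 16 weeks following study treatment". It then states that the true steady state of vector-derived FVIII can be assessed only "after a minimum of 72 hours has elapsed since the last infusion of FVIII protein concentrates". Section 9.7.2 asks sites, as a best effort, to "obtain FVIII activity measurements when a 72-hour interval without FVIII use is achieved". The visit-schedule footnotes and Section 12 repeat this through Year 7. None of these places derives the 72 hours, gives an acceptable residual, or distinguishes between products.

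The half-life statements stand elsewhere and do not agree. Section 7: "The short half-life for FVIII (~8-12 hours) necessitates frequent infusions". The same section on modified products: "Chemical modification or bioengineering of FVIII may improve half-life to 18-19 hours". Section 7.3: "half-life for FVIII (12-18 hours for most approved products) necessitates frequent infusions". Section 7.3 on longer-acting products: "FVIII-Fc fusion proteins) improve half-life by approximately 50" per cent.

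Section 9.4.8.1 lets subjects take FVIII whenever they need it. Neither the eligibility criteria (Sections 9.3.1 and 9.3.2) nor the prohibited-medication list (Section 9.4.8) limits which FVIII product that may be.

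**The concern.** A wash-out does its job only if what remains of the injected product is small against the threshold being tested. Here the threshold is low and one assay of two is enough, so a residual of a few IU/dL is as large as the endpoint itself. The protocol's half-lives differ more than twofold (8 h to 19 h), yet the interval does not move with them.

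Two readings are exposed. The first is the count of subjects at or above 5 IU/dL at Week 16. Planned cohorts hold at most four subjects (Cohorts 1-3) or six (Cohort 4), so one falsely counted responder moves a cohort's proportion by 1/4 = 25 or 1/6 = 17 percentage points. The second is duration: a subject whose expression has fallen and who has begun to treat bleeds may still read above 5 IU/dL at a later visit. Subjects with low expression can be expected to infuse more often, which would tilt the error towards weaker doses. That direction is plausible, but the protocol does not document it.

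**Working it through.** **Inputs from the protocol.** Interval 72 h (Sections 9.7.2 and 14.2). Threshold 5 IU/dL in either assay (Section 14.2). Half-lives 8-12 h and 18-19 h (Section 7) and 12-18 h (Section 7.3). Baseline endogenous FVIII 1 IU/dL or less (Section 9.3.1).

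**Assumptions.** First-order, single-phase decay after one infusion; repeated infusions would leave more. Post-infusion peak 50-100 IU/dL, because the protocol gives none. Its only level tied to exogenous FVIII is the pre-biopsy minimum of 50 IU/dL (Section 9.7.8), which is not a bleed-treatment peak.

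**No figure to reproduce.** The protocol states 72 h without any calculation or residual level.

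**Formulas.** Fraction left = 0.5^(72 / half-life). Residual = peak × fraction. Peak at which carry-over alone reaches the threshold = 5 / fraction.

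| Half-life | Half-lives in 72 h | Fraction left | Residual, peak 50-100 | Peak needed for 5 IU/dL |
|---|---|---|---|---|
| 8 h | 9.0 | 0.2% | 0.1-0.2 IU/dL | 2560 IU/dL |
| 12 h | 6.0 | 1.6% | 0.8-1.6 IU/dL | 320 IU/dL |
| 18 h | 4.0 | 6.25% | 3.1-6.3 IU/dL | 80 IU/dL |
| 19 h | 3.79 | 7.2% | 3.6-7.2 IU/dL | 69 IU/dL |

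If the subject also has 1 IU/dL of his own, only 4 IU/dL need be carried over: 4 / 0.0625 = 64 IU/dL at 18 h and 4 / 0.0723 = 55 IU/dL at 19 h. From a peak of 100 IU/dL, falling below 5 IU/dL takes half-life × log2(100/5): 52 h at 12 h, 78 h at 18 h and 82 h at 19 h.

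**Effect of five half-lives.** 0.5^5 = 3.1%, so a peak of 100 IU/dL leaves about 3 IU/dL. Carry-over alone would then need a peak of 5 / 0.03125 = 160 IU/dL. The time required is 5 × 18 = 90 h or 5 × 19 = 95 h.

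**Sensitivity to a longer half-life.** Adding the 50% gain of Section 7.3 to the 18 h upper end gives 18 × 1.5 = 27 h. The fraction left is then 0.5^2.67 = 15.7%, or 7.9-15.7 IU/dL. The protocol does not print 27 h. Applied to the 8-12 h of Section 7, the same gain gives 12-18 h, so the 12-18 h range may already contain it.

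**The case against.** **Half-lives give only a fraction.** Every IU/dL figure needs a peak the documents do not supply. This stands: the absolute residual is conditional. Even at 18 h, a peak of 50 IU/dL leaves 3.1 IU/dL, below the threshold.

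**A reader might infer that the protocol's own half-lives imply up to 16 IU/dL.** They do not. That figure needs the derived 27 h, while Section 7 puts modified products at 18-19 h and so caps the residual at about 7 IU/dL for a peak of 100.

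**Section 14.2 sets a minimum, not a guarantee.** Correct, and it does not say that any value at 72 h is wholly vector-derived. But the protocol states no further criterion, so in practice the minimum is the rule.

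**Section 9.7.2 confines the wash-out to subjects who have already reached 5 IU/dL at Week 16 and have not resumed standard replacement.** A subject with no expression therefore lies outside that instruction. This is a separate question of scope. The sentence in Section 14.2 carries no such limit, and for subjects inside the scope the interval is still too short for longer-acting products.

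**Value handling belongs to the SAP.** Partly so: Section 14.1 leaves detail to it and Section 14.9 lets it prevail. The 72 hours, however, is a number the protocol fixes, not one it leaves open.

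**There are safeguards.** FVIII use is recorded in the diary, activity and antigen are measured weekly through Week 36, prior pharmacokinetic information is collected (Section 12.2), and the analysis is descriptive in at most 15 subjects. A transient high value could be noticed, but nothing in the protocol says what would then be done with it.

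**Conclusion.** The point holds for longer-acting products only. At the protocol's upper half-lives of 18-19 h, 72 h leaves 6-7% of the peak, a result that rests only on first-order decay. With an assumed peak of 50-100 IU/dL this is about 3-7 IU/dL against a threshold of 5, and peaks of about 69-80 IU/dL or more reach the threshold by carry-over alone. For products at 8-12 h the residual is under 2 IU/dL and 72 h is adequate.

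A reader might go further and conclude that the wash-out fails for all products, or that responders have in fact been miscounted. The documents support neither: they do not show which products subjects used, at what peak, or how close to sampling. The half-life statements in Sections 7 and 7.3 conflict and must be reconciled, since the size of the residual depends on them. The matter merits a change to the rule, at modest priority.

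**What to change.** In Sections 9.7.2 and 14.2 and the visit footnotes, or in the SAP:

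- Keep 72 h for products with a half-life of about 12 h or less, and as the floor for all others.
- For longer-acting products, count a FVIII value towards the 5 IU/dL criterion and the duration summaries only if about five half-lives of the last product used have passed: 90-95 h at 18-19 h.
- Otherwise flag the value and use the nearest eligible scheduled sample.
- Report the responder count with and without flagged values. Missing data are not imputed (Section 14.1.2), so without this step frequent infusers could silently drop out.
- Confirm that product name and infusion time are captured. Section 9.4.8.1 (diary) and Section 9.7.8 (infusion eCRF pages) show that FVIII use is recorded, but not those two items.
- Reconcile the half-life statements in Sections 7 and 7.3.

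The Amendment 9 summary says recruitment is complete, so for Week 16 this can only be an analysis rule; it can be applied prospectively to the remaining follow-up. The added wait is 90 − 72 = 18 h to 95 − 72 = 23 h, well inside the visit windows of ±2 weeks (Years 2-5) and ±4 weeks (Years 6-7).

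The cost is a derived flag, some wording, and a few values that become ineligible. Around Week 16 a replacement is a week away. In Years 6-7 samples are 26 weeks apart, so there the with-and-without report carries more weight than substitution. The rule changes which value is analysed, not any subject's FVIII treatment.
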